4.3.2 Secondary outcomes

1. Neratinib treatment patterns will be described, including time to initiation after a trastuzumab based treatment, treatment dose, treatment duration, permanent and temporary discontinuation and reasons for treatment discontinuation or switch at the end of neratinib treatment as an extended adjuvant therapy for early-stage HER2+ breast cancer. All relevant information up to the end of the study observation period will be collected. Additionally, treatment

 Pierre Fabre TEMP CQA 0092 V2.0 Owning site : CORPORATE QA	Template to use for writing Corporate document, except Corporate policy and form, WORD in english	Page 18/ 29
--	--	-------------

persistence, median time to permanent discontinuation and median time to first dosage modification will also be evaluated via Kaplan-Meier estimates.

The following data will be collected to describe treatment patterns during neratinib use as an extended adjuvant therapy:

- End date of preceding trastuzumab treatment
- Initial dosage, Start and end date (if applicable)
- Dosage modifications (if applicable): dates, new dosage, reason for modification
- Neratinib discontinuation: date and reason for permanent or temporary discontinuation, duration of temporary discontinuation, subsequent treatment after discontinuation
- Subsequent treatment(s) upon disease recurrence or treatment discontinuation
- Concomitant endocrine therapy (for HR+ patients): type, start date, stop date
- Others concomitant treatment (if any): type, start date, stop date
- Corrective treatment for relevant AEs

2. Treatment history for breast cancer before neratinib initiation will be described. The following data will be collected:

- Prior anti-cancer drugs/therapies/procedures for breast cancer: type, medication name, start date and stop date
- Type of surgeries and date
- Radiotherapy after surgery (Yes/No): date and area
- Prior neoadjuvant and/or adjuvant anti HER2-directed therapy(ies) (including trastuzumab): type, start date and stop date
- Outcome of neoadjuvant/ treatment (if applicable): pathologic complete response (pCR) or no pCR
- Concomitant endocrine therapy

3. Frequency of relevant AEs during treatment with neratinib as an extended adjuvant therapy will be determined. Relevant AEs will be defined as all SAEs or AEs leading to dose adaptation or treatment discontinuation, and AEs of interest.

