7.7 Follow-up Period

The follow-up period for each patient extends from index date to end of the study observation period. Patients' data collection will be censored at date of death, or among patients who did not die, at the

end of the study observation period or at the date of last visit, whichever occurs first. Patients will have variable follow-up periods length, depending on their index date and last contact date.

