8.2 Time to Event Analysis

The cumulative incidence of events of interest will be assessed using the Kaplan Meier method and will be presented graphically (Kaplan Meier curve). For Kaplan-Meier, the number of events, number of censored data points, median survival time, Q1 and Q3 survival time and corresponding two-sided 95% CI will be presented. Estimates of the proportion of patients not presenting the event of interest at 3-month intervals (1, 3, 6, 9, 12, 15, 18 months) and the corresponding two-sided 95% CIs will be provided. Censoring rules relative to each event of interest are further detailed in the corresponding analysis sections (see section 13.2).

To determine the potential follow-up time the reverse Kaplan-Meier method will be applied, in this method the events and censors are reversed thus the event of interest (see section 13.2) becomes the censor. For the reverse Kaplan Meier, the number of events, number of censored data points, median follow-up time, Q1 and Q3 follow-up time and corresponding two-sided 95% CI will be presented.

If number of patients is large enough, Cox regression analysis may be performed to adjust for predefined baseline covariates. In this case and for time to Central Nervous System Metastasis, the Fine and Gray model will be used to account for the competing risk of disease recurrences.

Where applicable, the Log rank test will be used to compare time-to-event and survival data between subgroups in an exploratory manner.

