12 SECONDARY OUTCOMES

12.1 Neratinib Treatment Patterns

Neratinib treatment patterns will be described as frequencies and percentages or summary statistics, as appropriate, for FAS and by subgroup EU label; Pathologic stage; Residual disease after neoadjuvant treatment; Risk profile; Previous adjuvant or neoadjuvant therapy and Prior transtuzumab-based regimen overall and last treatment (Section 8.4).

For duration of neratinib treatment calculations, the date of first and last neratinib administration will be taken from the eCRF “Neratinib Treatment” form, variables “Neratinib Initiation date” and “Definitive discontinuation date” respectively. Interruptions, compliance, and dose changes are not considered for duration of neratinib treatment.

Neratinib treatment initiation details:

- Time from breast cancer diagnosis to neratinib initiation (months), calculated as:
 - $(Date\ of\ first\ neratinib\ administration - Date\ of\ diagnosis + 1) / 30.4$
- Time from completion of adjuvant trastuzumab-based therapy to neratinib initiation (months), calculated as:
 - $(Date\ of\ first\ neratinib\ administration - Date\ of\ completion\ of\ adjuvant\ trastuzumab-based\ therapy + 1) / 30.4$
- Performance status scale used at neratinib initiation: ECOG, Karnofsky, Other
 - If ECOG: 0, 1, 2, 3, 4, Unavailable
 - If Karnofsky: 100, 90, 80, 70, 60, 50, 40, 30, 20, 10, Unavailable and 90-100, 70-80, 50-60, 30-40, 10-20, Unavailable
- Performance status computed ECOG score (based on Table 3): 0, 1, 2, 3, 4, Unavailable
- Duration of neratinib treatment (months), calculated as:
 - For discontinued treatment,
 $(Date\ of\ last\ administration - Date\ of\ first\ administration + 1) / 30.4$

Document: ZZA65950_NEAR_SAP_v2.0

Author: [name]

Version Number: 2.0

Version Date: 22SEP2023

- For ongoing treatment, (*EOB date - Start date + 1*)
- Duration of neratinib treatment (categorized): ≤ 3 months, > 3 months to < 12 months, 12 months, >12 months
- Initial daily dosage (mg)
- Initial daily dose (mg), category: 40mg, 80mg, 120mg, 160mg, 200mg, 240mg, ...; and <240mg, 240mg, >240mg

Treatment modifications (dosage changes):

- Number and percentage of patients with at least one neratinib treatment modification. Percentage computed among FAS.
- Number of temporary modifications by patient
- Temporary modifications per patient category: 1, 2, >2. Percentage computed among FAS patients with at least one neratinib treatment modification.

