- Number and percentage of patients by reason for definitive discontinuation: Disease recurrence, Adverse event, Patient's wish, Physician's decision, Patient death, End of treatment period, Other. Percentage computed among FAS patients who discontinued neratinib treatment permanently.
 - Number and percentage of patients by switch onto another treatment following definitive discontinuation: Yes, No. Percentage computed among FAS patients who discontinued neratinib treatment permanently.

To supplement descriptions of neratinib treatment patterns for FAS, the Kaplan-Meier and reverse Kaplan Meier methods will be used. For Kaplan Meier, the number of events, number of censored data, median survival estimates will be reported along with the 1st and 3rd quartiles, and the corresponding two-sided 95% CI. Estimates of the proportion of patients not presenting the event of interest at 3-month intervals (1, 3, 6, 9, 12, 15, 18 months) and the corresponding two-sided 95% CIs. For the reverse Kaplan Meier, the number of events, number of censored data points, median follow-up time, Q1 and Q3 follow-up time and corresponding two-sided 95% CI will be presented. Kaplan Meier and reverse Kaplan Meier methods will be used for the following outcomes:

Document: ZZA65950_NEAR_SAP_v2.0

Author: [name]

Version Number: 2.0

Version Date: 22SEP2023

- Time from neratinib initiation to first temporary discontinuation (treatment persistence)
- Time from neratinib initiation to permanent treatment discontinuation⁽¹⁾
- Time from neratinib initiation to first treatment modification

⁽¹⁾ For the analysis of time to permanent discontinuation, death will be considered as an event.

Additionally, the Kaplan-Meier and reverse Kaplan Meier analysis will also be performed for permanent treatment discontinuation by subgroups Concomitant Prophylaxis Antidiarrheal and Initial Dose of Neratinib (section 8.4).

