13.2 Time to Event Analysis

All time to event outcomes described in the subsections below will be summarized using the Kaplan-Meier method as described in section 8.2, for FAS and by subgroup EU label; Previous adjuvant or neoadjuvant therapy; Residual disease after neoadjuvant treatment; Prior trastuzumab-based regimen overall; and Prior trastuzumab-based regimen last treatment. (section 8.4)

Patients for whom the event did not occur or who are lost to follow-up, will be censored at the last recorded date that the patient is known to be alive. For patients alive at end of study will be considered the date of study entry, for patients who withdraw consent will be considered the date of consent withdrawal, for patients lost to follow-up will be considered the date of last contact, as collected in the eCRF.

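### SAP 12.1 does not say how permanent discontinuation or death is handled in the Kaplan-Meier analysis of time to first treatment modification, so the figures depend on how the SAP is read

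*SAP*

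**What the plan says.** Protocol 4.3.2 makes this a secondary outcome: "median time to first dosage modification will also be evaluated via Kaplan-Meier estimates". SAP 12.1 carries it forward as "Time from neratinib initiation to first treatment modification" and asks for a median, quartiles, estimates at 1, 3, 6, 9, 12, 15 and 18 months, and a reverse Kaplan-Meier summary. In SAP 12.1 a modification is a change of dosage, tabulated separately from temporary and permanent discontinuation.

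Four places bear on censoring:

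- The only footnote to the SAP 12.1 outcomes concerns a different one: "For the analysis of time to permanent discontinuation, death will be considered as an event".
- SAP 8.2 sends the reader elsewhere: "Censoring rules relative to each event of interest are further detailed in the corresponding analysis sections (see section 13.2". Section 13.2 limits itself to "All time to event outcomes described in the subsections below", and its tables cover iDFS, DDFS, CNS metastasis and OS. Its default is "Patients for whom the event did not occur or who are lost to follow-up, will be censored at the last recorded date" on which the patient is known to be alive.
- The general rule in SAP 7.7 is that patients' "data collection will be censored at date of death, or among patients who did not die, at the" close of observation or last visit, whichever is earlier. SAP 7.8 defines the end of observation (EOB) in similar terms. Neither mentions stopping neratinib.
- SAP 8.2 ties the Fine and Gray model to the optional Cox analysis and to CNS metastasis, and names recurrence as the competing risk.

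**The concern.** A patient who stops neratinib for good, or dies, with the dosage unchanged can no longer have a dosage change. This will be common. Protocol section 2 gives a one-year course, and SAP 12.1 lists the end of the treatment period as a reason for definitive discontinuation, so permanent stop is the expected exit for most unmodified patients.

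Two programmers could follow this SAP faithfully and produce different curves. One ends time at risk at permanent stop, and so assumes that stoppers would later have been modified at the same rate as those still on drug. The other keeps everyone to EOB. The 12-month proportion, the median, the numbers at risk at months 15 and 18, and the reverse Kaplan-Meier follow-up all change with that choice. Under the first rule the reverse Kaplan-Meier describes roughly time on drug; under the second, calendar follow-up. SAP 12.1 also applies plain Kaplan-Meier to time to first temporary discontinuation, where the same gap exists.

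**Working it through.** **1. Yardstick from the plan.** The documents give no modification or stopping rates. The only design figures are the precisions in SAP 4.2 for 120 patients, which reproduce:

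- at 50%: 1.96 × √(0.5 × 0.5 / 120) = 8.95 points (stated ±9%)
- at 30%: 1.96 × √(0.3 × 0.7 / 120) = 8.20 points (stated ±8.2%)

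**2. Censoring at permanent stop.** Let M be the true 12-month cumulative incidence of a first modification, and S that of stopping or dying before any modification. Both are assumed, with constant cause-specific hazards.

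- Total cumulative hazard: L = −ln(1 − M − S)
- Modification part: h = L × M / (M + S)
- Reported proportion: 1 − KM = 1 − exp(−h), to be compared with M
- Kaplan-Meier median in months: 12 × ln 2 / h

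| M | S | L | h | 1 − KM | Excess (points) |
|---|---|---|---|---|---|
| 30% | 10% | 0.511 | 0.383 | 31.8% | +1.8 |
| 30% | 25% | 0.799 | 0.436 | 35.3% | +5.3 |
| 30% | 40% | 1.204 | 0.516 | 40.3% | +10.3 |
| 40% | 10% | 0.693 | 0.555 | 42.6% | +2.6 |
| 40% | 25% | 1.050 | 0.646 | 47.6% | +7.6 |
| 40% | 35% | 1.386 | 0.739 | 52.3% | +12.3 |
| 40% | 40% | 1.609 | 0.805 | 55.3% | +15.3 |

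In the last two rows the Kaplan-Meier median is 12 × 0.693 / 0.739 = 11.25 months and 12 × 0.693 / 0.805 = 10.3 months. In both, only 40% have been modified by month 12.

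**3. Keeping patients to EOB.** The last index date is 31 December 2020 (SAP 7.1) and the common cut-off is 05 July 2022 (SAP 7.5). That is 551 days, so minimum potential follow-up is (551 + 1) / 30.4 = 18.2 months. Without early loss or death nobody is censored before month 18, and 1 − KM is simply the number modified divided by the number of patients.

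**4. Both rules on the same simulated data.** There were 120 patients and 2,000 repetitions. Hazards were front-loaded over the first two months, everyone stopped by month 12, and EOB was uniform between 18.1 and 59 months. All rates were assumed.

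| Modified | Stopped first | 12-month 1 − KM, censored at stop | 12-month 1 − KM, kept to EOB | At risk at month 15: stop / EOB |
|---|---|---|---|---|
| 30.9% | 12.0% | 32.9% | 30.9% | 0 / 83 |
| 32.2% | 19.3% | 36.4% | 32.2% | 0 / 81 |
| 33.0% | 33.0% | 41.6% | 32.9% | 0 / 80 |

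The two rules differ by 2.0, 4.2 and 8.7 points. At these modification rates the median was rarely or never reached under either rule, so a spuriously reached median needs higher rates, as in the last two rows of step 2.

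**The case against.** A reader might infer that the SAP censors at permanent stop and so will clearly overstate both the rate and the median. The documents do not support this. No section censors at stop. Where SAP 12.1 is silent, the natural rules to borrow are SAP 7.7 and 7.8, or the default in 13.2, and all of them keep stopped patients in the denominator. Step 3 shows that this comes close to the cumulative incidence one would want. Death is at least covered by the general rule, as a censoring point; the real silence is on permanent stop. The direction for the median is also the reverse: under stop-censoring it is shortened. Nor does a higher proportion modified necessarily mean worse tolerability, because SAP 12.1 counts escalations as modifications too.

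Three further points carry weight. On-treatment Kaplan-Meier is a recognised quantity if it is labelled as such. The larger excesses rest on assumed rates, and with 10% stopping first the excess is 2 to 3 points. These curves supplement a study that Protocol 4.3 calls purely descriptive, and SAP 12.1 also reports the crude percentage of the full analysis set with at least one modification.

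What remains is that neither reading is written down and the on-treatment quantity is not labelled. The crude percentage does not settle the matter: under stop-censoring one report could show 40% crude and 52.3% by Kaplan-Meier for the same event, with no explanation.

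**Conclusion.** The gap is real, and the overstatement is conditional on the reading. If permanent stop is censored, the 12-month proportion is too high by about 2 to 5 points (30% modified, 10-25% stopping unmodified) or about 8 to 15 points (40% modified, 25-40% stopping unmodified). The upper range is comparable with, or larger than, the plan's own ±9-point precision. The median is then too short or is reached when it should not be, and almost no one is at risk at months 15 and 18, where estimates are planned. If patients are kept to EOB, the overstatement from stopping largely disappears. Only censored deaths are left, presumably few in this early-stage population (an assumption). The sizes rest on assumed rates and constant hazards; the simulation with front-loaded hazards gives the same picture. Severity is minor.

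**What to change.** In SAP 12.1, for time to first treatment modification and for time to first temporary discontinuation:

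- Replace plain Kaplan-Meier with the Aalen-Johansen cumulative incidence, with permanent discontinuation (any reason, including end of treatment) and death as competing events.
- Report it at the planned 1, 3, 6, 9, 12, 15 and 18 months. The curve stays defined after most patients have left treatment.
- Quote an overall median only if the cumulative incidence reaches 50%. Label any median among modified patients as a descriptive summary only.
- Record the change in SAP 7.10, because Protocol 4.3.2 names Kaplan-Meier. If the database is already locked, report it as a deviation under Protocol 4.7.1.

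The change is safe under either reading: it gives nearly the same curve if EOB censoring was meant, and removes a bias if stop-censoring was meant. The cost is a short SAP amendment and a SAS option; no new data are needed. The downside is that an overall median may not be quotable.

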12.1.1 Performance Status Changes

The change in performance status will be analyzed in 3 months intervals from neratinib initiation (from index to month 1, 3, 6, 9, 12) until end of observation date (section 7.8). This analysis will be presented as ECOG scale, if the performance status is collected in the eCRF with the Karnofsky scale, it will be mapped to the corresponding ECOG score [2], using the conversions in Table 3.

Table 3 Performance Scales Conversion Table

ECOG Score	Karnofsky Grade
0	90 to 100
1	70 to 80
2	50 to 60
3	30 to 40
4	10 to 20
5	0

12.2 Concomitant Treatments

Concomitant treatments will be analyzed over the whole follow-up period. For each therapy type of concomitant treatment [Endocrine therapy, Prophylaxis antidiarrheal and Corrective antidiarrheal therapy in response to AE (diarrhea)], the following variables will be presented for FAS:

- Number and percentage of patients with at least one treatment of the therapy type. Percentage computed among FAS.
- Number and percentage of patients by treatment name. Percentage computed among FAS patients with at least one treatment of the concomitant therapy type.
- Duration of treatment (months)*, calculated as:
 - For discontinued treatments, $(End\ date - Start\ date + 1) / 30.4$
 - For ongoing treatments, $(EOB\ date - Start\ date + 1) / 30.4$

*A patient can contribute with multiple treatments for the same therapy type, the duration of treatment will correspond to the total exposure of the patient to the treatment type.

Note: Other specified treatment names will be coded with WHO Drug version B3 March 2021, the reported and coded terms will be presented in a listing.

For concomitant treatment of Corrective therapy in response to other relevant AE, the following variables will be presented:

- Number and percentage of patients with at least one treatment. Percentage computed among FAS.
- Number and percentage of patients by adverse event description. Percentage computed among FAS patients with at least one corrective therapy in response to other relevant AE.
- Number and percentage of patients by treatment name, as ATC 5th level coded with WHO Drug. Percentage computed among FAS patients with at least one corrective therapy in response to other relevant AE.
- Number and percentage of patients with at least one maximum dosage received. Percentage computed among FAS patients with at least one corrective therapy in response to other relevant AE.
- Duration of treatment (days), calculated as:
 - For discontinued treatments, $(End\ date - Start\ date + 1)$

- For ongoing treatments, (*EOB date - Start date + 1*)

*A patient can contribute with multiple treatments; the duration of treatment will correspond to the total exposure of the patient to the treatment type.

Note: For corrective therapy in response to other relevant AE, the dose, dose unit and frequency, are also collected in the CRF. These details will be presented in a listing.

12.3 Breast Cancer Treatment History

Breast cancer treatment history will be described based on the neoadjuvant and adjuvant therapies, surgeries, and radiotherapy the patient received before neratinib initiation.

12.3.1 Neoadjuvant and Adjuvant Therapy

The following variables will be presented as frequencies and percentages and summary statistics as appropriate, for neoadjuvant therapy (pre-surgery) and adjuvant therapy (post-surgery), separately, for FAS and by subgroup EU label; Pathological stage; Risk profile (section 8.4). For adjuvant therapy analysis will also be performed by subgroup Previous adjuvant or neoadjuvant therapy (section 8.4).

- Number and percentage of patients with at least one therapy. Percentage computed among FAS.
- Number of therapies by patient
- Number and percentage of patients by therapy combinations of any therapy type. Percentage computed among FAS.
- Number and percentage of patients by therapy combination category: Chemotherapy (+/- Endocrine therapy), Chemotherapy + Trastuzumab (+/- Endocrine therapy), Chemotherapy + Trastuzumab + Pertuzumab (+/- Endocrine Therapy), TDM1 (+/- Endocrine therapy) (for adjuvant only) and Other (+/- Endocrine therapy).
- Duration of treatment (months)⁽¹⁾, calculated as:
 - (*End date - Start date + 1*) / 30.4
- Outcome: pCR, No pCR (for the neoadjuvant therapy overall)

- Number and percentage of patients by neoadjuvant/adjuvant therapies received. Percentage computed among FAS.
- For each therapy type (Chemotherapy, Endocrine Therapy, Anti-HER2, Immunotherapy, Other):
 - Number and percentage of patients by therapy name. Percentage computed among FAS with each treatment type.
 - Number and percentage of patients by therapy combination. Percentage computed among FAS with each treatment type.
 - Duration of treatment (months)⁽¹⁾, defined as:
 - $(End\ date - Start\ date + 1) / 30.4$
 - Number and percentages of patients who stopped the treatment as initially planned: Yes, No
 - If no, the reason: Toxicity, Worsening condition, No response/ Partial response, Physician's decision, Patient's wish, Other
 - Outcome: pCR, No pCR (in neoadjuvant therapy only)

⁽¹⁾A patient can contribute with multiple therapies, the duration of treatment will correspond to the total exposure of the patient to the treatment type.

Additionally, for anti-HER2, the therapy combinations will also be presented.

In the adjuvant setting, for anti-HER2, the number and percentage of patients by Prior trastuzumab-based regimen (last treatment) will be presented.

Note: Immunotherapy names and other specified therapy names will be coded with WHO Drug version B3 March 2021, the reported and coded terms will be presented in a listing and the preferred term will be presented in the respective table.

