4.3.4 Subgroups of interest

The following subgroups are of interest, based on patient characteristics at neratinib initiation (index date) or primary diagnosis of breast cancer. Analyses of primary, secondary, and exploratory outcomes may be performed for some or all of these subgroups, subject to pertinence and the number of patients in each subgroup.

1. Nodal status at initial diagnosis (0, 1-3, ≥ 4), Tumor size at initial diagnosis (T1, T2, \geq T3), Stage I vs Stage II+III
 - a. Low risk (Stage I and N- or pCR) vs high risk (Stage II/III or N+ or no pCR)
2. Previous adjuvant or neoadjuvant therapy (Yes/No)
3. Residual disease after neoadjuvant treatment (no pCR)
4. Prior trastuzumab-based regimen (trastuzumab only/ trastuzumab and pertuzumab/ T-DM1)

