8.4 Examination of Subgroups

The following subgroups are of interest, based on patient characteristics at neratinib initiation (index date) or primary diagnosis of breast cancer. Analyses of primary, secondary, and exploratory outcomes may be performed for some or all these subgroups, subject to pertinence and the number of patients in each subgroup:

- EU label status: Yes, No
 - Yes, defined as, HR+ patients with initiation of Neratinib ≤ 1 year from trastuzumab-based treatment completion in adjuvant setting (EU Label population)
 - No, otherwise
- Pathologic stage (AJCC classification) at primary breast cancer: Stage I, Stage II+III
 - If missing, derived as in 2
- Residual disease after neoadjuvant treatment (pathologic complete response [pCR]): pCR, No pCR

- Risk: Low risk (Stage I or N- or pCR), High risk (Stage II/III or N+ or no pCR)
 - N-, defined as, the electronic case report form (eCRF) nodal status category of NX or N0
 - N+, defined as $N \geq 1$ nodal
- Previous adjuvant or neoadjuvant therapy ⁽²⁾: Neoadjuvant + Post neoadjuvant treatment, Adjuvant only
 - Neoadjuvant + Post neoadjuvant, defined as, at least one neoadjuvant and one adjuvant treatment
 - Adjuvant only, defined as, at least one adjuvant treatment and no neoadjuvant
- Prior trastuzumab-based regimen overall (neoadjuvant or adjuvant): Trastuzumab only, Trastuzumab and Pertuzumab, Trastuzumab emtansine (T-DM1), Other anti HER2
- Prior trastuzumab based regimen the last treatment in adjuvant setting before Neratinib initiation: Trastuzumab only, Trastuzumab and Pertuzumab, Trastuzumab emtansine (T-DM1), Other anti HER2
- Hormone Receptor at Primary Breast Cancer Diagnosis: HR+, HR-
 - HR+, defined as either ER or PR or both are positive
 - HR-, defined as if ER and PR are negative
- Concomitant Corrective Antidiarrheal: Yes, No
- Concomitant Prophylaxis Antidiarrheal: Yes, No
- Initial Dose of Neratinib: <240mg, 240mg, >240mg

Table 2 AJCC staging

Primary tumor (T)	Regional lymph nodes (N)	Distant metastasis (M)	Stage
Tis	N0	M0	0
T1	N0	M0	IA
T0	N1	M0	IB
T1	N1	M0	IB
T0	N1	M0	IIA
T1	N1	M0	IIA
T2	N0	M0	IIA
T2	N1	M0	IIB
T3	N0	M0	IIB
T0	N2	M0	IIIA
T1	N2	M0	IIIA
T2	N2	M0	IIIA
T3	N1	M0	IIIA
T3	N2	M0	IIIA
T4	N0	M0	IIIB
T4	N1	M0	IIIB
T4	N2	M0	IIIB
Any T	N3	M0	IIIC
Any T	Any N	M1	IV

N2 and N3 are not collected in the CRF, this regional lymph node categories will be identified by “ ≥ 4 ” lymph nodes involved.

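### SAP 12.3.1 tabulates pCR by a Risk profile that pCR itself helps to define, so the contrast between the risk columns is built in

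*SAP*

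**What the plan says.** SAP 12.3.1 presents its neoadjuvant and adjuvant therapy variables "for FAS and by subgroup EU label; Pathological stage; Risk profile (section 8.4"). Among those variables are the neoadjuvant result overall, "Outcome: pCR, No pCR (for the neoadjuvant therapy overall"), and the same result within each therapy type, "Outcome: pCR, No pCR (in neoadjuvant therapy only").

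SAP 8.4 defines the risk subgroup as "Risk: Low risk (Stage I or N- or pCR), High risk (Stage II/III or N+ or no pCR"). Its node terms are "N-, defined as, the electronic case report form (eCRF) nodal status category of NX or N0" and "N+, defined as $N \geq 1$ nodal". It gives no rule for a patient who satisfies both lists.

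Protocol 4.3.4 words the Low class differently: "Low risk (Stage I and N- or pCR) vs high risk (Stage II/III or N+ or no pCR"). SAP 7.10 does not list this change from the protocol.

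**The concern.** A row variable that is also a criterion for the column cannot give an informative contrast between columns. Here a pCR patient always satisfies the Low list and a no-pCR patient always satisfies the High list. A table laid out this way will tend to show more pCR in Low than in High even if response is unrelated to stage and nodal status. Someone reading it as response by disease risk would take a product of the classification for a finding.

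This is separate from the overlap between the two classes. Adding a precedence rule, the natural remedy for the overlap, does not remove the circularity. If either list is put first, the circularity becomes exact.

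**Working it through.** The documents state no pCR rate or other figure on this point, so there is nothing of theirs to reproduce. The check is a logical enumeration, followed by an illustration on assumed rates.

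**Inputs.** The Low and High lists from SAP 8.4; the rows and columns from SAP 12.3.1; the denominator from SAP 8.1, which computes percentages among patients with available data. Adjuvant-only patients have no pCR result and drop out.

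**Step 1: patients counted in both columns.** Let *a* be the number of pCR patients and *b* the number of no-pCR patients.

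- Low holds all *a*, plus only those *b′* ≤ *b* no-pCR patients who are Stage I or N-. Its rate is *a*/(*a* + *b′*) ≥ *a*/(*a* + *b*).
- High holds all *b*, plus only those *a′* ≤ *a* pCR patients who are Stage II/III or N+. Its rate is *a′*/(*a′* + *b*) ≤ *a*/(*a* + *b*).

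The direction is therefore fixed before any data are seen. The same argument applies within each therapy type.

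**Step 2: enumeration.** Crossing stage (I, II/III), node (N-, N+) and outcome (pCR, no pCR) gives 8 profiles, of which 6 meet both lists. Only Stage I / N- / pCR is Low alone, and only Stage II/III / N+ / no pCR is High alone. The table counts profiles, not patients.

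| Patients who meet both lists | Low: pCR / no pCR | High: pCR / no pCR | Forced result |
|---|---|---|---|
| Counted in both columns | 4 / 3 | 3 / 4 | Direction only |
| High list first | 1 / 0 | 3 / 4 | Low 100% pCR |
| Low list first | 4 / 3 | 0 / 1 | High 0% pCR |
| Dropped | 1 / 0 | 0 / 1 | Low 100%, High 0% |

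Allowing stage or node to be missing (18 profiles, 10 in both lists) leaves the last column unchanged.

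**Step 3: protocol wording.** Read as (Stage I and N-) or pCR, the forced results are the same. Read as Stage I and (N- or pCR), High first still gives Low 100% pCR, but Low first leaves both columns mixed (Low 2 / 1, High 2 / 3). SAP 12.3.1 refers to SAP 8.4, so the SAP definition is the one that applies.

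**Step 4: illustration.** Assume, with no support in the documents, that stage, node and pCR are independent, with Stage I 20–40%, N- 40–60% and pCR 30–50%. For 20%, 40% and 30%:

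- Low share = 1 − 0.8 × 0.6 × 0.7 = 0.664; pCR in Low = 0.3/0.664 = 45.2%.
- High share = 1 − 0.2 × 0.4 × 0.3 = 0.976; pCR in High = (0.3 − 0.024)/0.976 = 28.3%.
- In both = 0.664 + 0.976 − 1 = 64.0%.

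Over the corners of the assumed ranges, 64–78% of patients are in both classes, pCR is 36–66% in Low and 25–48% in High, and within each scenario Low exceeds High by about 11 to 18 percentage points (smallest 38.7 − 27.4 = 11.3; largest 65.8 − 47.9 = 17.9). By assumption the true association is nil.

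**The case against.** The strongest reply is that the plan is purely descriptive and that SAP 8.4 bases subgroups on status at primary diagnosis or at neratinib initiation. By the index date the pCR result is known, so Risk is a legitimate composite and a pCR row within it merely shows how each class is made up. SAP 8.4 also leaves subgroup analyses optional, depending on relevance and numbers, and SAP 9 defers the layout to table shells that are not available here, so the row may never be produced. These arguments limit the importance of the point. They do not remove it: 12.3.1 names Risk profile for these rows and carries no warning. It does leave out the residual-disease subgroup used in 11.1, 11.3 and 12.1, yet keeps Risk profile, which contains the same variable.

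A reader might infer that one column must be exactly 100% or 0% pCR under the text as written. The documents do not support that. SAP 8.4 states no precedence, and with double counting only the direction is fixed. Some rules that make the classes exclusive also force nothing, for example letting stage decide and using node or pCR only when stage is missing.

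A reader might also infer that response by initial extent of disease goes unreported. It does not, because Pathological stage is already a planned subgroup for these same rows.

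**Conclusion.** The circularity is real under the SAP 8.4 definition, and the pCR rows by Risk profile cannot be read as a finding. With double counting, the rate in Low is at or above the overall rate and the rate in High is at or below it. An exact 100% in Low or 0% in High needs a further condition: one list takes precedence over the other, or overlapping patients are dropped.

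These statements rest on the available-data denominator of SAP 8.1 and apply only to neoadjuvant patients with a recorded outcome. The 11-to-18-point gap is an illustration on assumed rates, not a prediction. No test, sample size or primary outcome is affected, so this is a low-severity improvement.

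**What to change.** In SAP 12.3.1 and the matching table shells, omit the pCR / No pCR rows from the Risk profile columns, both overall and by therapy type. Keep them for the full analysis set and by Pathological stage.

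A breakdown by nodal status at diagnosis is optional. The data are collected (SAP 11.3), but SAP 7.10 removed nodal status from the subgroups of interest, so adding it back should be acknowledged there. It should also say how NX is handled, since SAP 8.4 groups NX with N0.

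The cost is one sentence in the SAP and an edit to the shells. No new data are needed and no interpretable information is lost. Resolving the overlap in SAP 8.4 is a separate task and does not replace this change.
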